9.9 Analysis visit windows

For endpoints to be reported by visit, the following analysis visit windows will be defined:

- Baseline (see Section 9.3 for definition)
- Analysis Day 2
- Analysis Day 3
- Analysis Day 4
- Analysis Day 5: Day 5 and 6
- Analysis Day 7: Day 7 and 8
- Analysis Day 10: from Day 9 to Day 11
- Analysis Day 14: from Day 12 to Day 17
- Analysis Day 21: from Day 18 to Day 24
- Analysis Day 28: from Day 25 to Day 35
- Analysis Day 44: from Day 36 to Day 52
- Analysis Day 60: from Day 53 onwards

In case of multiple assessments collected within the same window, the one closest to the target date will be used for summary statistics. All the assessments will be used for worst case analyses.

10 Study Participants

The subsections in this section include specifications for reporting participant disposition and study treatment/study discontinuations. Additionally, procedures for reporting protocol deviations are provided.

10.1 Disposition of Participants and Discontinuations

Disposition information will be collected in the ‘Demography’, ‘Exposure’, ‘End of Study Treatment’ and ‘Disposition’ eCRF pages.

The number and percentage of participants in each of the below disposition categories will be presented by actual treatment group for the enrolled analysis set. Percentages will be presented with respect to the number of treated participants

- Total number of participants enrolled (i.e. participants who gave informed consent)
- Number of participants who discontinued from the study prior to randomization overall and grouped by the main reason (e.g. the failed specific inclusion or exclusion criteria, withdrawal of consent)

- Number of randomized participants.

The treatment status will be summarized as follows:

- Number and percentage of participants who did not receive any dose of study treatment
- Number and percentage of participants who took at least one dose of study treatment.

The end of treatment status will be summarized by:

- Number and percentage of treated participants who completed study treatment (defined as participants which completed the full course of the study as per 'End of Study Treatment' eCRF page).
- Number and percentage of treated participants who discontinued the study treatment, overall and by primary reason.

The end of study status will be summarized by number and percentage of treated participants who completed or prematurely discontinued the study after randomization, grouped by main reason.

Additionally, the number of participants enrolled, and treated in each analysis set will be provided overall, by country and by site.

The results of the randomization algorithm (according to IWRS) will be summarized as follows:

- Cross tabulation: participants randomized (Placebo / M5049 50 mg BID / M5049 100 mg BID) vs. treated (Placebo / M5049 50 mg BID / M5049 100 mg BID)
- Cross tabulation: participants randomized to each stratum according to the IWRS vs. stratum according to the eCRF

The following listings will be created to report disposition information:

- Subject disposition: presenting information related to informed consent signature, protocol version, randomization and screen failure status for the enrolled analysis set
- Discontinued subjects: presenting information of treatment and study discontinuation for the ITT/SAF analysis set
- Randomization scheme: presenting information on randomization and analysis strata for all the subjects randomized or treated.

10.2 Protocol Deviations / Exclusion from Analysis Populations

10.2.1 Important Protocol Deviations

Important protocol deviations (IPDs) are protocol deviations that might significantly affect the completeness, accuracy, and/or reliability of the study data or that might significantly affect a participant's rights, safety, or well-being.

They will be identified for all participants by either site monitoring, medical review processes or programming and confirmed prior to or at the Data Review Meeting at the latest.

All important protocol deviations are documented in SDTM datasets whether identified through site monitoring, medical review or programming.

A full list of potential protocol deviations including definition and categorization is maintained in the most recent study protocol deviation guide.

Important protocol deviations will be summarized by category.

A listing of important protocol deviations will be provided based on the ITT/SAF.

10.2.2 Reasons Leading to the Exclusion from an Analysis Population

A listing presenting reasons of exclusion from PK/PD analysis sets will be provided.

11 Demographics and Other Baseline Characteristics

If not stated otherwise, the following analyses will be performed based on the ITT/SAF, by treatment groups and overall.

11.1 Demographics

Demographic characteristics and physical measurements will be summarized descriptively using the following information from the ‘Demography’ and ‘Screening Vital Signs’ eCRF pages.

The following demographic characteristics will be included:

- Sex: male, female
- Race: white, black or African American, Asian/ Pacific Islander, American Indian or Alaska Native, more than one race, other, unknown
- Ethnic origin: Hispanic or Latino/Not Hispanic or Latino
- Age (years)
- Age categories:
 - < 60 years,
 - ≥ 60 years
- Country: Brazil, Philippines, United States of America
- Site
- Height (cm) at Baseline

- Weight (kg) at Baseline
- BMI (kg/m²) at Baseline
 - < 30 kg/m²,
 - ≥ 30 kg/m²

Specifications for computation:

- Age [years]
 - (date of given informed consent - date of birth + 1) / 365.25
 - In case of missing day for at least one date, but month and year available for both dates: For the derivation of age, the day of informed consent and the day of birth will be set to 1 and the formula above will be used
 - In case of missing month for at least one date, but year available for both dates: For the derivation of age, the day and the month of informed consent and the day and month of birth will be set to 1 and the formula above will be used

The integer part of the calculated age will be used for reporting purposes.

- BMI [kg/m²] = $\frac{\text{weight [kg]}}{\text{height[cm]}^2} \times 10000$

All demographic data will be reported in listings.

11.2 Medical History

The medical history will be summarized from the “Medical History” eCRF page, using MedDRA version 23.0 or higher, preferred term (PT) as event category and system organ class (SOC) body term as Body System category. Each participant will be counted only once within each PT or SOC.

Medical history will be displayed in terms of frequency tables, ordered by primary SOC and PT in alphabetical order, and listed.

11.3 Other Baseline Characteristics

Tobacco consumption will be collected in the ‘Substance Usage’ eCRF page. The following information will be summarized together with demographic characteristics:

- Tobacco Status;

The following disease history characteristics will be summarized overall and by treatment group:

- Based on data from ‘Medical History’ eCRF page
 - Time since COVID-19 symptoms onset (days)
 - Time since diagnosis (days)

- Presence of the following co-morbidities:
 - Diabetes
 - Heart disease
 - Obstructive lung disease
 - Other lung disease
 - Chronic liver disease
 - HIV
 - Tuberculosis
 - Central nervous system disease
 - Hypertension
- Based on data from ‘COVID Symptom Assessment’ eCRF page
 - Presence of each of the following COVID-19 symptoms at study entry
 - Cough
 - Fever
 - Myalgia
 - Diarrhea
 - Dyspnea
 - Fatigue/malaise
 - Loss of appetite
 - Loss of smell
 - Loss of taste

‘Time since’ disease history characteristics, in days, will be calculated as follows:

- Time since symptoms onset (days) = (Date of first administration of study treatment - Date of symptoms onset)
- Time since diagnosis (days) = (Date of first administration of study treatment - Date of diagnosis)

The following listings will be created:

- Tobacco use
- Co-morbidities

- COVID symptoms.

Baseline characteristics with respect to vital signs, and hematology/biochemistry will be part of Section 15 (Safety Analysis).

12 Previous or Concomitant Medications/Procedures

The following analyses will be performed based on the ITT/SAF analysis set by study treatment group.

Concomitant treatments are medications, other than study treatment, which are taken by participants any time during the on-treatment period, see Section 9.7.

Previous medications are medications, other than study treatment, which started before first administration of study treatments.

A medication may be classified as both concomitant and previous. The respective flags will be derived based on start and end date.

Partially or completely missing medication start and stop dates will be handled as described in Section 9.8.

Previous and concomitant treatments will be summarized separately by number and percentage of participants from the “Concomitant medications” eCRF page. Anatomical Therapeutic Chemical classification (ATC) 2nd level and preferred term will be tabulated as given from the WHO-DD dictionary most current version. If any medication is classified into multiple ATC classes, the medication will be summarized separately under each of these ATC classes. The summary tables will be sorted by decreasing frequency of drug class and decreasing frequency of drug name in a given drug class in the total column. In case of equal frequency regarding drug class (respectively drug name), alphabetical order will be used. In case any specific medication does not have an ATC classification level 2 coded term, it will be summarized under “UNCODED ATC classification” category. Each participant will only be counted once per medication, even if he/she received the same medication at different times.

All medications (prior, and concomitant) will be listed.

All **concurrent procedures**, collected in the “Related Procedures” eCRF page, will be coded using MedDRA version 23.0 or higher and reported in listings.

13 Study Treatment: Compliance and Exposure

The following analyses will be performed based on the ITT/SAF analysis set by treatment group.

All dosing calculations and summaries will be based on “Exposure” eCRF page. Each participant is expected to be treated with the drug assigned by the randomization system for 14 consecutive days, twice per day.

In case of discharge from the hospital before the end of treatment period, the participant will be instructed to take the study treatment at home and a diary card will be handled to collect daily dosing information.

In case the start date is missing or incomplete, it is assumed that the first dose of study treatment is given at the randomization date.

Duration of exposure to study drug (days) = (end date/time – date/time of first dose of study drug), where end date/time is the date/time of last dose of study drug.

Dose administered at each administration will be derived as follows:

- Participants randomized to M5049 50 mg = number of tablets administered * 12.5 mg
- Participants randomized to M5049 100 mg = number of tablets administered * 25 mg

Cumulative dose is the sum of all doses administered.

Compliance will be derived using information from ‘Drug accountability’ eCRF page.

Compliance (%) = $100 \times (\text{Number of tablets taken} / \text{Number of planned tablets to be taken})$

where:

- Number of tablets taken = (total number of tablets dispensed – total number of tablets returned)
- Number of planned tablets = Planned duration of exposure (i.e. 14 days) × Number of planned tablets per day (i.e. 8 tablets/day) = 112 tablets

In case of study drug not returned and amount returned missing, it will be assumed that all tablets have been taken for compliance calculation. Considering that 120 tablets are dispensed to ensure the subject has sufficient stock, compliance for subjects not returning any tablet will be $107\% = 120/112 * 100$.

The summary of treatment exposure will include the following information:

- Exposure duration (days)
- Cumulative dose (mg)
- Compliance (%)

A separate listing will be presented for:

- Treatment exposure
- Drug accountability
- Exposure and compliance parameters
- Subjects receiving investigational product(s) from specific kits.

14 Efficacy Analyses

The following analyses will be performed based on the ITT by treatment group except when otherwise stated.

For the time to event analysis, failure will be defined as follows:

| Definition | eCRF page | Value |
|--|--|--|
| Invasive or Non-Invasive Mechanical Ventilation | Ordinal Scale on Clinical Severity | Ordinal Scale on Clinical Severity >= 5 |
| ICU admission leading to treatment discontinuation (both the following conditions) | End of study treatment AND Hospitalization | Did the subject complete the full course of study treatment? = NO AND Date of treatment completion/discontinuation occurring during ICU/HDU stay |
| Relapse | Date of Visit | Reason for Relapse completed |

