9.1.2 Efficacy Assessments

For all Baseline assessments and Follow-up Visits, refer to [Table 1](#) for procedures to be done and details for each assessment. The respiratory status is assessed on a daily basis together with the clinical status on the WHO ordinal scale. The clinical response (efficacy assessment) is based on data collected from the primary endpoint time to recovery from first dose (Day 1) through Day 28 (defined as first occurrence of WHO scale 3 or less) and assessments of respiratory status and the clinical ordinal scale for secondary endpoints are performed on Days 1 through Day 28.

The FiO₂ score and method of respiratory support will be obtained (e.g., nasal cannula, high flow oxygenation, noninvasive ventilation, mechanical ventilation, etc.) from the hospital chart and recorded for the day obtained (i.e., on Day 4, Day 4 respiratory status is obtained and recorded as Day 4). For participants who are placed on invasive mechanical ventilation, document the reason for intubation and the local institutional protocol for intubation.

In addition, both SpO₂ measured by pulse oximetry and FiO₂ will be recorded at the time SpO₂ is documented on a daily basis while the participant is hospitalized. When SpO₂ reaches $\geq 94\%$ in room air and is maintained for 24 hours, the day and time are recorded at the beginning and conclusion of the 24 hours, as documentation is supportive of the primary endpoint (i.e., alive and free of respiratory support).

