9.1.3 Secondary Endpoint Assessments

9.1.3.1 Clinical Status

The clinical status will be assessed with an ordinal scale as the second assessment of a given study day. The score can be obtained from the hospital chart using the last score prior to the time of assessment. This is recorded for the day obtained (i.e., on Day 3, Day 3 score is obtained and recorded as Day 3).

The WHO ordinal scale is as follows:

0. Uninfected: no clinical or virological evidence of infection.
1. Ambulatory: no limitation of activities.
2. Ambulatory: limitation of activities.
3. Hospitalized, mild disease: hospitalized, no oxygen therapy.
4. Hospitalized, mild disease: oxygen by mask or nasal prongs.
5. Hospitalized, severe disease: noninvasive ventilation or high flow-oxygen.
6. Hospitalized, severe disease: intubation and mechanical ventilation.
7. Hospitalized, severe disease: ventilation + additional organ support – e.g., pressors, rapid response team, ECMO.
8. Death.

When deaths are recorded, data should be collected on whether the death occurred after withdrawal of care and, if so, the reason for withdrawal of care.

9.1.3.2 Additional Clinical Endpoints, COVID-19 Inflammatory Biomarkers, and Select Serum Biomarkers

Data collected for other clinical endpoint and inflammatory biomarkers will be obtained from the participant's hospital chart and should be recorded for the day obtained. Where relevant, data will also be cross-checked with the SAE and AE reported data (e.g., all-cause mortality as an SAE report).

As part of the secondary clinical endpoint assessments, data on all-cause mortality (Day 1 through Day 60), the time to ICU (Day 1 through Day 28), the time to invasive mechanical ventilation (Day 1 through Day 28), the time to noninvasive mechanical ventilation (Day 1 through Day 28), the total days in ICU from Day 1 through Day 60, and the total days in the hospital from Day 1 through Day 60 will be collected for analysis.

Inflammatory biomarker data (C-reactive protein, d-dimer, and ferritin) collected by the site during the study period (Day 1 through Day 28) will also be recorded as indicated in [Table 1](#) in the study clinical database. Other biomarker data and research samples analyzed at the central laboratory are not established as standard of care and will not be available for participant management.

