10.4.2 Analysis of the Primary Efficacy Endpoint

The primary endpoint, time to recovery, is defined as the time from first dose (Day 1) through Day 28 to first occurrence of WHO 9-point ordinal scale 3 or less. For participants who die and those considered as failure (that includes use of mechanical ventilation, ICU admission leading to treatment discontinuation, and relapse), the time to recovery will be censored at Day 28. For participants completing the study without recovering or failure, the time to recovery will be censored at Day 28. Participants withdrawn before the End of Study Visit without recovering or failure will be censored at the last date of available clinical status assessment.

Cumulative distribution function for time to recovery will be estimated via the Kaplan-Meier (product-limit estimates) method by treatment group and presented together with associated statistics (median time to recovery, recovery rates at Day 7, Day 14, and Day 28) including the corresponding two-sided 95% CI.

The potential intercurrent events that could confound the primary endpoint are:

- Intensive care unit admission/invasive mechanical ventilation/death.
- Treatment discontinuation due to AE.
- Concomitant medication: antiviral therapy including convalescent plasma, corticosteroids.
- Forbidden concomitant medication (e.g., chloroquine-related medications, immunomodulating drugs).

Specific analyses to account for intercurrent events and stratification factors will be described in the IAP.

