14.2.2 Clinical Status

Clinical status will be based on data collected on the ‘Ordinal Scale for Clinical Status’ eCRF page and is assessed with the following ordinal scale:

0. Uninfected: no clinical or virological evidence of infection.
1. Ambulatory: no limitation of activities.
2. Ambulatory: limitation of activities.
3. Hospitalized, mild disease: hospitalized, no oxygen therapy.
4. Hospitalized, mild disease: oxygen by mask or nasal prongs.
5. Hospitalized, severe disease: noninvasive ventilation or high-flow oxygen.
6. Hospitalized, severe disease: intubation and mechanical ventilation.
7. Hospitalized, severe disease: ventilation + additional organ support – e.g., pressors, RRT, ECMO
8. Death.

In case of death, the participant will be counted with the clinical status =8 (death) for any scheduled timepoint after death date. There will be no imputation of missing data.

Clinical status is expected every day during hospitalization and then at every scheduled visit after discharge. Day 1 assessment will serve as baseline measurement. If missing, the last non-missing measurement prior to randomization will be used.

The number and percentage of participants in each clinical status category as well as summary statistics for absolute and change from baseline status will be presented by treatment group, in a tabular and graphical form, using a stacked bar chart.

A cumulative logit model will be used to compare the clinical status results of each M5049 group versus placebo at the following analysis visits: Day 7, Day 14, Day 21, Day 28, Day 44 and Day 60 according to the ordinal scale described above. Under the assumption of proportional odds, the odds ratio (OR) and its 95% Wald CI will be estimated for each M5049 group versus placebo. A score test for the proportional odds assumptions will be reported.

Should the model fail, due to an insufficient number of observations per category of the dependent variable, then relevant categories may be collapsed.

In addition, the following dichotomized versions of the clinical status will be derived, only if at least 6 participants in each level are present:

- Death (clinical status = 8) versus any other category (clinical status \neq 8)
- Worsening (clinical status \geq 5) versus stable/improvement (clinical status $<$ 5)
- In-hospital (clinical status \geq 3) versus hospital discharged (clinical status $<$ 3).

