14.2.6 Time to Non-Invasive Mechanical Ventilation (Day 1 Through Day 28)

Time to non-invasive mechanical ventilation will be based on data collected on the ‘Ordinal Scale for Clinical Severity’ eCRF page.

Time to non-invasive mechanical ventilation is defined as the time from first dose (Day 1) to the date/time of clinical status ≥ 5 , in days:

- Time to non-invasive mechanical ventilation (days) = (Date/time of clinical status ≥ 5 – Date/time of first dose)

The rules below to define censoring/event dates will be followed:

| # | Description | Date of Event or Censoring | Outcome |
|---|--|---|----------|
| 1 | Clinical status ≥ 5 or Death from Day 1 up to D28 | Earliest between date of clinical status ≥ 5 and date of death (as applicable) | Event |
| 2 | For subjects which never started mechanical ventilation and not died | Earliest between D28 and date of discontinuation | Censored |

Analyses will be performed as specified in Section [14.2.5](#).

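### The SAP codes ventilation failure as an ordinal score of 5 or more, so participants who had only high-flow oxygen and then recovered count as never recovered

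*SAP*

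**What the plan says.** Protocol 10.4.2 censors at Day 28 the participants who die and "those considered as failure (that includes use of mechanical ventilation, ICU admission leading to treatment discontinuation, and relapse". High-flow oxygen is not named.

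SAP Section 14 turns this into a table of failure definitions that applies to the time-to-event analyses. The ventilation row is labelled "Invasive or Non-Invasive Mechanical Ventilation", and its only criterion is "Ordinal Scale on Clinical Severity >= 5" on the ordinal-scale eCRF page.

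The content of score 5 is the same in both documents. SAP 14.2.2 has "Hospitalized, severe disease: noninvasive ventilation or high-flow oxygen", and protocol 9.1.3.1 has "Hospitalized, severe disease: noninvasive ventilation or high flow-oxygen".

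The failure definition enters rule 2 of the censoring tables for time to recovery (SAP 14.1.1), time to SpO2 improvement (14.2.3) and time to hospital discharge (14.2.9). A failure at any time from Day 1 to Day 28 gives censoring at Day 28. Separately, SAP 14.2.6 reads "Time to non-invasive mechanical ventilation is defined as the time from first dose (Day 1) to the date/time of clinical status" of 5 or more, with death also counted as an event.

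Protocol 9.1.2 requires the method of respiratory support to be recorded: "e.g., nasal cannula, high flow oxygenation, noninvasive ventilation, mechanical ventilation, etc".

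**The concern.** The coded rule is wider than the event it is meant to implement. Both the protocol text and the SAP label say ventilation, while the code says ventilation or high-flow oxygen. SAP Section 7, which lists departures from the protocol's planned analyses, mentions only the stratification factors.

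A participant who needs high-flow oxygen for a day or two, steps down and comes off oxygen has recovered as protocol 3.2 defines it. Under the SAP coding that participant stays in the risk set to Day 28 with no event. The primary analysis then loses true recoveries and understates the recovery rate. Its hazard ratio mixes speed of recovery with avoidance of high-flow oxygen. The trial enrols patients with pneumonia and low room-air saturation who are not yet ventilated, so escalation to high-flow oxygen is a foreseeable course.

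**Working it through.** The documents show no power, effect size or event count against which to check this point. The check is therefore a reading of the rules followed by an illustration of size.

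**1. Is high-flow oxygen ventilation in these documents?** Protocol 9.1.2 lists it as its own method. That list also separates noninvasive from mechanical ventilation, so it does not settle the matter alone. Inclusion criterion 5 does: it describes mechanical ventilation as invasive or noninvasive and does not mention high-flow oxygen. Mechanical ventilation thus includes noninvasive ventilation, and nothing extends it to high-flow oxygen.

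**2. Does failure override recovery?** The SAP does not write the order. Rule 5 (score of 3 or less gives an event) lacks the no-failure condition that rules 6 and 7 carry. Failure must still take precedence, for three reasons:
- Relapse is a failure, and by SAP 14.2.12 it can occur only after discharge, which is a score below 3. If recovery took precedence, listing relapse would do nothing.
- Rule 1 censors at Day 28 for death up to Day 60, so it too is built to override a recovery.
- Protocol 10.4.2 censors failures at Day 28 without condition.

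**3. A test participant.** Scores on Days 1-8 are 4, 4, 5, 5, 4, 4, 4, 3, with score 5 due to high-flow oxygen only.

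| Ventilation failure derived from | Outcome |
|---|---|
| Score 5 or more (SAP) | Censored at Day 28 as a failure |
| Recorded noninvasive or invasive ventilation | Recovery event on Day 8 |

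A cut-off of 6 or more gives the same answer here but would miss noninvasive ventilation, so moving the cut-off is not enough.

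**4. Events, rate and precision.** From the documents: 150 participants at 1:1:1, so 50 per arm. Assumed: 70% recover by Day 28, 10-20% have high-flow oxygen only, and 60% of those recover.
- Lost recoveries per arm = 50 x P(high-flow only) x P(recover given high-flow only): 50 x 0.10 x 0.6 = 3, and 50 x 0.20 x 0.6 = 6.
- Day 28 rate: 0.70 - 3/50 = 0.64, and 0.70 - 6/50 = 0.58.
- The standard error of the log hazard ratio varies as 1/sqrt(events): sqrt(0.70/0.64) = 1.046, and sqrt(0.70/0.58) = 1.099.
- Wider range: 50 x 0.05 x 0.4 = 1 to 50 x 0.20 x 0.8 = 8 events lost per arm.

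**5. Median and hazard ratio.** Here the assumption is exponential recovery with 85% recovered by Day 28 in both arms, so the daily rate is -ln(0.15)/28 = 0.0678. A share h of participants, chosen independently of recovery, is recoded as failures. The median solves (1 - h)(1 - exp(-0.0678 t)) = 0.5. It is 10.2 days at h = 0, and 11.0, 12.0 and 14.5 days at h = 5%, 10% and 20%.

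Cox hazard ratios were simulated with 100,000 participants per arm and no true difference in recovery:

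| High-flow-only share, placebo | Share, active | Hazard ratio under SAP coding |
|---|---|---|
| 10% | 10% | 1.00 |
| 10% | 5% | 1.12 |
| 20% | 10% | 1.23 |
| 5% | 10% | 0.90 |
| 10% | 20% | 0.81 |

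**The case against.** The best opposing reading is that a threshold of 5 was intended and only the label is poor. The scale calls score 5 severe disease, SAP 14.2.2 uses the same cut for worsening, and the protocol's wording on failure is not clearly exhaustive. This is possible, but the plan does not say it. Both documents name ventilation in the failure rule. If escalation to high-flow oxygen is meant to count, the protocol and the label have to say so.

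Other points stand in part:
- **Rule order is inferred, not written.** True, and the SAP should state it. The mislabelling of 14.2.6 does not depend on it.
- **The protocol itself censors ventilated participants who later recover.** True. Only participants with high-flow oxygen and no ventilation belong to this point.
- **The size is assumed, and the direction is not fixed.** Also true. With equal high-flow use in the arms the simulated hazard ratio stays at 1.00. With unequal use it moves either way, so the coding is not reliably conservative.
- **Other analyses keep these recoveries.** The responder analysis (14.2.1) and the cumulative logit model (14.2.2) use the score on the day. They do not repair the primary endpoint, and the same participant can be a responder in one table and unrecovered in another.
- **A redacted sensitivity analysis may deal with this.** It may, but the primary derivation is visible and would not change.
- **The trial is exploratory, with no confirmatory testing.** This lowers the regulatory stakes. It does not make the primary endpoint match its definition.

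**Conclusion.** The concern holds. The ventilation failure as coded contradicts its own label and the protocol, and it turns some protocol-defined recoveries into non-events in the primary analysis and in two secondary time-to-event analyses. Time to noninvasive ventilation in SAP 14.2.6 is in fact time to high-flow oxygen, any ventilation or death.

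The mismatch is certain from the text; its size is not, because no rate of high-flow use is given. Under the stated assumptions it costs 3-6 recoveries per arm of 50 (1-8 over the wider range) and lowers the Day 28 rate by 6-12 percentage points. A twofold difference between arms in high-flow use would alone shift a null hazard ratio to about 0.81-1.23. It needs correcting before database lock because it determines which participants have a primary event.

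**What to change.** 1. In SAP Section 14, derive the ventilation failure from the recorded method of respiratory support: noninvasive or invasive ventilation recorded, or an ordinal score of 6 or 7. Score 5 with high-flow oxygen only is not a failure. Deaths remain under rule 1.
2. Use the same source for 14.2.6, or rename it as time to high-flow oxygen, ventilation or death.
3. State in 14.1.1, 14.2.3 and 14.2.9 that the death and failure rules take precedence over the event rule.
4. Say what happens when the method of support is missing or conflicts with the ordinal score.
5. If high-flow escalation was meant to be a failure, keep the cut-off, rename the failure, align protocol 10.4.2 and record the change in SAP Section 7.

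The cost is SAP wording and one derivation. Protocol 9.1.2 already requires the method of support, and SAP 14.2.3 already draws on a 'Respiratory Status' eCRF page. The fields on that page are not shown, so the sponsor should first confirm that it separates high-flow oxygen from noninvasive ventilation.
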